10.0 Adverse Event (AE) Reporting and Monitoring

10.1 Adverse Event Characteristics

CTCAE term (AE description) and grade: The descriptions and grading scales found in the revised NCI Common Terminology Criteria for Adverse Events (CTCAE) version 4.0 will be utilized for AE reporting. All appropriate treatment areas should have access to a copy of the CTCAE version 4.0. A copy of the CTCAE version 4.0 can be downloaded from the CTEP web site: (http://ctep.cancer.gov/protocolDevelopment/electronic_applications/ctc.htm)

- 10.11 Adverse event monitoring and reporting is a routine part of every clinical trial. First, identify and grade the severity of the event using the CTCAE version 4.0. Next, determine whether the event is expected or unexpected (see Section 10.2) and if the adverse event is related to the medical treatment or procedure (see Section 10.3). With this information, determine whether the event must be reported as an expedited report (see Section 10.4).

Important: Expedited adverse event reporting requires submission of a MedWatch 3500A report(s). Expedited reports are to be completed within the timeframes and via the mechanisms specified in Sections 10.2 and 10.3. All AEs reported via expedited mechanisms must also be reported via the routine data reporting mechanisms defined by the protocol (see Sections 10.5 and 18.0).

10.12 Each CTCAE term in the current version is a unique representation of a specific event used for medical documentation and scientific analysis and is a single MedDRA Lowest Level Term (LLT).

- NOTE: A severe AE, as defined by the above grading scale, is NOT the same as serious AE which is defined in the table in Section 10.4.

10.2 Expected vs. Unexpected Events

- The determination of whether an AE is expected is based on agent-specific information provided in Section 15.0 of the protocol.
- Unexpected AEs are those not listed in the agent-specific information provided in Section 15.0 of the protocol.

NOTE: “Unexpected adverse experiences” means any adverse experience that is neither identified in nature, severity, or frequency of risk in the information provided for IRB review nor mentioned in the consent form.

10.3 Assessment of Attribution

When assessing whether an adverse event is related to a medical treatment or procedure, the following attribution categories are utilized:

- Definite - The adverse event *is clearly related* to the agent(s).
- Probable - The adverse event *is likely related* to the agent(s).
- Possible - The adverse event *may be related* to the agent(s).
- Unlikely - The adverse event *is doubtfully related* to the agent(s).
- Unrelated - The adverse event *is clearly NOT related* to the agent(s).

Events determined to be possibly, probably or definitely attributed to a medical treatment suggest there is evidence to indicate a causal relationship between the drug and the adverse event.

10.31 **Special Situations for Expedited Reporting**

Exceptions to Expedited Reporting: EXPECTED Serious Adverse Events

An expedited report may not be required for specific Grade 1, 2 and 3 Serious Adverse Events where the AE is **EXPECTED**. Any protocol specific reporting procedures **MUST BE SPECIFIED BELOW** and will supersede the standard Expedited Adverse Event Reporting Requirements:

Note: These exceptions only apply if the adverse event does not result in hospitalization.

If the adverse event results in hospitalization, then the standard expedited adverse events reporting requirements must be followed.

System Organ Class (SOC)	Adverse event/Symptoms	CTCAE Grade at which the event will not be expeditiously reported.
Gastrointestinal Disorders	Diarrhea	Any Grade
	Dyspepsia	
	Nausea	
	Vomiting	
	Colitis	Grades 1-3
	Pancreatitis	
General disorders and administrations site conditions	Anorexia	Any Grade
	Asthenia	
	Dehydration	
	Fatigue	
	Malaise	
	Weight loss	
Hepatobiliary disorders	Cholecystitis	Grades 1-3
Infections and infestations	Lung Infection	Grades 1-3
	Sinusitis	
	Skin infection	
	Urinary tract infection	
Investigations	Alkaline phosphatase increased	Any Grade
	Alanine aminotransferase increased	
	Aspartate aminotransferase increased	
	Lymphocyte count decreased	
Metabolism and nutrition disorders	Hyperkalemia	Any Grade
	Hypocalcemia	
	Hypomagnesemia	
	Hyponatremia	
Musculoskeletal and connective tissue disorders	Arthralgia	Any Grade
	Back pain	
	Musculoskeletal and connective tissue disorder – Other (muscle spasms)	
Skin and subcutaneous tissue disorders	Alopecia	Any Grade
	Rash acneiform	
	Rash maculo-papular	
	Palmar-plantar erythrodysesthesia syndrome	

10.311 Persistent or Significant Disabilities/Incapacities

Any AE that results in persistent or significant incapacity or substantial disruption of the ability to conduct normal life functions (formerly referred to as disabilities), congenital abnormalities or birth defects, must be reported immediately if they occur at any time following treatment with an agent under an IND/IDE since they are considered to be a serious AE and must be reported to the sponsor as specified in 21 CFR 312.64(b).

10.312 **Death**

- Any death occurring within 30 days of the last dose, regardless of attribution to an agent/intervention under an IND/IDE requires expedited reporting within 24-hours.
- Any death occurring greater than 30 days with an attribution of possible, probable, or definite to an agent/intervention under an NCI IND/IDE requires expedited reporting within 24-hours.

- **Reportable categories of Death**
 - Death attributable to a CTCAE term.
 - Death Neonatal: A disorder characterized by cessation of life during the first 28 days of life.
 - Death NOS: A cessation of life that cannot be attributed to a CTCAE term associated with Grade 5.
 - Sudden death NOS: A sudden (defined as instant or within one hour of the onset of symptoms) or an unobserved cessation of life that cannot be attributed to a CTCAE term associated with Grade 5.
 - Death due to progressive disease should be reported as **Grade 5 “Neoplasms benign, malignant and unspecified (incl cysts and polyps) – Other (Progressive Disease)”** under the system organ class (SOC) of the same name. Evidence that the death was a manifestation of underlying disease (e.g., radiological changes suggesting tumor growth or progression; clinical deterioration associated with a disease process) should be submitted.

10.313 **Secondary Malignancy**

- A *secondary malignancy* is a cancer caused by treatment for a previous malignancy (e.g., treatment with investigational agent/intervention, radiation or chemotherapy). A secondary malignancy is not considered a metastasis of the initial neoplasm.
- All secondary malignancies that occur following treatment with an agent under an IND/IDE to be reported. Three options are available to describe the event:
 - Leukemia secondary to oncology chemotherapy (e.g., Acute Myelocytic Leukemia [AML])
 - Myelodysplastic syndrome (MDS)
 - Treatment-related secondary malignancy
- Any malignancy possibly related to cancer treatment (including AML/MDS) should also be reported via the routine reporting mechanisms outlined in each protocol.

10.314 **Second Malignancy**

- A second malignancy is one unrelated to the treatment of a prior malignancy (and is NOT a metastasis from the initial malignancy). Second malignancies require ONLY routine reporting.

10.4 Expedited Reporting Requirements for Studies using Commercial Agent(s) ONLY:

Expedited Reporting Requirements for Adverse Events that Occur in a Non-IND/IDE trial within 30 Days of the Last Administration of a Commercial Agent^{1,2}

FDA REPORTING REQUIREMENTS FOR SERIOUS ADVERSE EVENTS (21 CFR Part 312)

NOTE: Investigators **MUST** immediately report to the sponsor **ANY** Serious Adverse Events, whether or not they are considered related to the investigational agent(s)/intervention (21 CFR 312.64)

An adverse event is considered serious if it results in **ANY** of the following outcomes:

- 1) Death
- 2) A life-threatening adverse event
- 3) An adverse event that results in inpatient hospitalization or prolongation of existing hospitalization for ≥ 24 hours
- 4) A persistent or significant incapacity or substantial disruption of the ability to conduct normal life functions
- 5) A congenital anomaly/birth defect.
- 6) Important Medical Events (IME) that may not result in death, be life threatening, or require hospitalization may be considered serious when, based upon medical judgment, they may jeopardize the patient or subject and may require medical or surgical intervention to prevent one of the outcomes listed in this definition. (FDA, 21 CFR 312.32; ICH E2A and ICH E6).

ALL SERIOUS adverse events that meet the above criteria **MUST** be immediately reported to the sponsor within the timeframes detailed in the table below.

Hospitalization	Grade 1 Timeframes	Grade 2 Timeframes	Grade 3 Timeframes	Grade 4 & 5 Timeframes
Resulting in Hospitalization ≥ 24 hrs	7 Calendar Days			24-Hour 3 Calendar Days
Not resulting in Hospitalization ≥ 24 hrs	Not required	7 Calendar Days		

NOTE: Protocol specific exceptions to expedited reporting of serious adverse events are found in section 10.31 of the protocol.

Expedited AE reporting timelines are defined as:

- “24-Hour; 3 Calendar Days” - The AE must initially be reported via MedWatch within 24 hours of learning of the AE, followed by a complete expedited report within 3 calendar days of the initial 24-hour report.
- “7 Calendar Days” - A complete expedited report on the AE must be submitted within 7 calendar days of learning of the AE.

¹Serious adverse events that occur more than 30 days after the last administration of investigational agent/intervention and have an attribution of possible, probable, or definite require reporting as follows:

Expedited 24-hour notification followed by complete report within 3 calendar days for:

- All Grade 4, and Grade 5 AEs

Expedited 7 calendar day reports for:

- Grade 2 adverse events resulting in hospitalization or prolongation of hospitalization
- Grade 3 adverse events

² For studies using PET or SPECT IND agents, the AE reporting period is limited to 10 radioactive half-lives, rounded UP to the nearest whole day, after the agent/intervention was last administered. Footnote “1” above applies after this reporting period.³

Effective Date: May 5, 2011

Additional Instructions:

1. An increased incidence of an expected adverse event (AE) is based on the patients treated for this study at their site. A list of known/expected AEs is reported in the package insert or the literature, including AEs resulting from a drug overdose.
2. Submit form 3500A to the FDA, MedWatch, [name], by fax at [name] or online at <http://www.fda.gov/Safety/MedWatch/HowToReport/default.htm>.
3. **ACCRU Sites:** Follow site-specific reporting guidelines. Provide copies by fax [REDACTED] to the ACCRU SAE Coordinator. The ACCRU SAE Coordinator will then electronically send the report to Bayer:

Electronic Mailbox: [REDACTED]

Facsimile: [REDACTED]

Address: [REDACTED]

Mail only [REDACTED]

Address: [REDACTED]

FDX or UPS only: [REDACTED]

Reports for all Bayer products can also be phoned in via our Medical Communications Department

Phone: [REDACTED]

The Site Investigator shall report to ACCRU within 24 hours of the investigator's awareness of other events such as:

- An adverse event related to study specific procedures
- Any new and important event related to treatment with the study drug(s).
- Any pregnancy during which a female patient was exposed to the study drug(s)
- Any pregnancy in the partner of a male patient, where the male patient was exposed to study drug at the time of conception or conception occurred within two weeks of the last dose of study drug(s).
- Any other relevant safety information including but not limited to reports on drug interaction, overdose, drug abuse or misuse, drug dependency, withdrawal syndrome, medication error, occupational exposure and lack of drug effect (LODE) occurring at any time during the treatment phase.

Pregnancy: If a pregnancy occurs, follow the patient throughout the pregnancy until the outcome of the pregnancy is available. Subsequent follow-up will depend on the outcome of the pregnancy. If there is an abnormal outcome or pregnancy complications, additional follow-up may be requested to obtain further information.

Any communication concerning safety related information to regulatory authorities or ethics committees including but not limited to:

- Development Safety Update Reports (DSUR) / relevant parts of IND reports for the STUDY;
- Any other safety related reports, issues and queries that are either raised by or communicated to regulatory authorities or ethics committees;

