- b) Distribution – Regorafenib undergoes enterohepatic circulation with multiple plasma concentration peaks observed across the 24-hour dosing interval. Regorafenib is highly bound (99.5%) to human plasma proteins.
- c) Metabolism – Regorafenib is metabolized by CYP3A4 and UGT1A9. The main circulating metabolites measured at steady state are M-2 (N-oxide) and M-5 (N-oxide and N-desmethyl), both of them having similar *in vitro* pharmacological activity and steady-state concentrations as regorafenib. M-2 and M-5 are highly protein bound (99.8% and 99.95%, respectively).

d) Excretion – Elimination half-lives for regorafenib and the M-2 metabolite in plasma are 28 hours (14 to 58 hours) and 25 hours (14 to 32 hours), respectively. M-5 has a longer mean (range) elimination half-life of 51 hours (32 to 70 hours). Elimination occurs through: Feces (71%; 47% as parent compound; 24% as parent compound; 24% as metabolites); Urine (19%).

15.16 **Potential Drug Interactions:** Avoid concomitant use of strong CYP3A4 inducers (i.e. rifampin, phenytoin, carbamazepine, phenobarbital and St. John's Wort) and strong CYP3A4 inhibitors (i.e. clarithromycin, grapefruit juice, itraconazole, ketoconazole, posaconazole, telithromycin and voriconazole).

15.17 **Known potential toxicities:**

Serious Adverse Effects:

Hepatotoxicity: [U.S. Boxed Warning]: Severe liver toxicity and hepatic failure (sometimes resulting in death) have been observed in clinical trials; hepatocyte necrosis with lymphocyte infiltration has been demonstrated with liver biopsy. Monitor hepatic function at baseline and during treatment. Interrupt therapy for hepatotoxicity; dose reductions or discontinuation are necessary depending on the severity and persistence.

Most Common Adverse Events, >10%

Cardiovascular: Hypertension

Central nervous system: Fatigue, dysphonia, pain, fever, headache.

Dermatologic: Palmar-plantar erythrodysesthesia, rash, alopecia

Endocrine & metabolic: Hypocalcemia, hypophosphatemia, hyponatremia, hypokalemia, hypothyroidism

Gastrointestinal: Appetite decreased, lipase increased, diarrhea, mucositis, weight loss, amylase increased, nausea, vomiting

Hematologic: Anemia, lymphopenia, thrombocytopenia, INR increased, hemorrhage, neutropenia

Hepatic: AST increased, ALT increased, hyperbilirubinemia

Neuromuscular & skeletal: Stiffness

Renal: Proteinuria

Miscellaneous: Infection

Less Common Adverse Events, 1% - 10%

Cardiovascular: Myocardial ischemia and infarction

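### Section 10.31 limits the expedited-report exemption to expected Grade 1-3 serious events, but its table exempts 25 of 32 terms at Any Grade and includes 12 terms that Section 15 does not list

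*Combined protocol and SAP*

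**What the plan says.** The opening sentence of Section 10.31 sets two conditions. The first is a grade limit: "An expedited report may not be required for specific Grade 1, 2 and 3 Serious Adverse Events". The second is that the event is expected. A note adds a third: "Note: These exceptions only apply if the adverse event does not result in hospitalization". Procedures specified below that sentence "will supersede the standard Expedited Adverse Event Reporting Requirements", and Section 10.4 refers back to 10.31 for its exceptions.

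The table that follows has a column headed "CTCAE Grade at which the event will not be expeditiously reported". For most terms the entry is Any Grade; for the rest it is Grades 1-3. The Investigations block, which includes "Alanine aminotransferase increased" together with AST and alkaline phosphatase, is Any Grade.

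Expectedness is defined in Section 10.2: "Unexpected AEs are those not listed in the agent-specific information provided in Section 15.0 of the protocol". Section 15.17 lists ALT and AST increases as common and carries a boxed warning: "Severe liver toxicity and hepatic failure (sometimes resulting in death) have been observed in clinical trials".

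Section 10.4 sets a 24-hour notice and a complete report within 3 further calendar days for Grade 4 and 5 serious events, and 7 calendar days for most lower-grade ones.

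**The concern.** A site reading 10.31 meets two grade limits for the same exemption. The sentence keeps Grade 4 events on the expedited route. The table takes many of them off it and is given precedence over 10.4. Section 10.4 also tells investigators to report every serious event to the sponsor at once, before deferring to 10.31. Two sites could therefore handle the same event differently and each point to protocol text.

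The list also has a problem of its own. An exemption reserved for expected events names several that are unexpected under the protocol's own definition.

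What is at stake is the speed and uniformity of safety reporting. The trial has no toxicity stopping rule (16.5), and DSMB reports come every six months (16.7). The primary analysis is not affected.

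**Working it through.** No sample size, power or error rate is involved. The check is a count of the table, a match against Section 15, and a trace of one event through the reporting rules.

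**1. Grade entries in the 10.31 table.**

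| Group | Any Grade | Grades 1-3 |
|---|---|---|
| Gastrointestinal | 4 | 2 (colitis, pancreatitis) |
| General disorders | 6 | 0 |
| Hepatobiliary | 0 | 1 (cholecystitis) |
| Infections | 0 | 4 |
| Investigations | 4 | 0 |
| Metabolism | 4 | 0 |
| Musculoskeletal | 3 | 0 |
| Skin | 4 | 0 |
| Total | 25 | 7 |

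25 + 7 = 32 terms. The 25 entries conflict with the sentence; the 7 agree with it. The 25 counts labels, not terms where a Grade 4 event will arise. For PPES, for example, the grading table in Section 8.3 stops at Grade 3.

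**2. Match against Section 15 (15.17 and 15.27).**

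- Listed by name or plain synonym, 13: diarrhea, nausea, vomiting, anorexia, fatigue, weight loss, ALT, AST, lymphocyte count decreased, hypocalcemia, hyponatremia, alopecia, PPES.
- Covered only by a generic word, 7: the four infections, back pain, two rash types.
- Not listed, 12: dyspepsia, colitis, pancreatitis, asthenia, dehydration, malaise, cholecystitis, alkaline phosphatase increased, hyperkalemia, hypomagnesemia, arthralgia, muscle spasms.

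13 + 7 + 12 = 32. Of the 12, three (colitis, pancreatitis, cholecystitis) are exempt at Grades 1-3, and 12 - 3 = 9 at Any Grade. Section 15.17 lists hypokalemia, the opposite of the exempted hyperkalemia.

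The match involves judgment. A generous reader might place asthenia and malaise under fatigue, dyspepsia under reflux, and arthralgia and muscle spasms under pain or stiffness. That leaves 12 - 5 = 7 unlisted: colitis, pancreatitis, cholecystitis, dehydration, alkaline phosphatase, hyperkalemia and hypomagnesemia.

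**3. One event traced.** Take an ALT or AST rise above 20 times the upper limit of normal, which Table 8.35 places at Grade 4. Suppose it is judged serious (life-threatening or an important medical event) and the patient is not hospitalized.

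| Rule | Result |
|---|---|
| 10.31 sentence | Grade 4 is outside the exemption, so 10.4 applies |
| 10.4 | 24-hour notice, complete report within 3 further calendar days |
| 10.31 table | No expedited report |
| 10.522 | Case report form entry, whatever the attribution |

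ALT and AST are listed in Section 15, so only the grade conflict touches them. Alkaline phosphatase is affected by both defects.

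**The case against.** A reader might infer that Grade 4 liver events can go unreported. The documents do not support that.

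- Section 10.31 waives only the expedited report. Section 10.522 still requires every Grade 3 and 4 event on the case report form.
- The waiver ends if the event results in hospitalization, and deaths remain expedited under 10.312.
- Hyperbilirubinemia, liver failure and severe liver injury are not in the exemption table, so most of what the boxed warning describes keeps the standard timelines.
- The timelines in 10.4 apply to serious events, and 10.12 warns that severe is not the same as serious. An outpatient Grade 4 laboratory value that meets no seriousness criterion was never on the 24-hour clock.
- Liver monitoring and treatment decisions for the individual patient under Table 8.35 do not depend on expedited reports.

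Nor is the six-monthly DSMB report the only review. Section 16.45 provides for adverse event reports to go to an outside reviewer 1-2 times per month, and 10.4 asks sites to report any new and important treatment-related event to the coordinating group within 24 hours.

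A second objection is that the table may state the real intent. Within the gastrointestinal group it deliberately separates Any Grade from Grades 1-3, and the sentence could be leftover template text. That is possible, and the documents do not settle it. It leaves the contradiction in place.

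A third is that expectedness may rest on more than Section 15. The note in 10.2 also refers to information given for IRB review and to the consent form, Section 15.0 points to the investigator brochure, and 10.4 mentions the package insert and literature. Those sources were not available for this check and could support some of the 12 terms. The definition in 10.2 nevertheless names Section 15.0 of the protocol, and on that definition the terms fail.

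**Conclusion.** Both inconsistencies stand. The grade limit in the 10.31 sentence conflicts with 25 of the 32 table entries, and 12 of the 32 terms (7 on a generous match) do not meet the exemption's condition of being expected under 10.2.

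The practical gap is narrow. For the liver tests it is a serious Grade 4 rise in ALT, AST or alkaline phosphatase without hospitalization, which on the table's reading would miss the 24-hour/3-day report but not routine recording. This should be corrected because it is a conflicting safety rule that sites must apply, and correction is cheap.

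The conclusion rests on two readings of tables broken in extraction. Any Grade is taken as a merged cell covering the whole Investigations block, because it is the only grade entry there. The 24-hour/3-day entry in 10.4 is taken to cover Grade 4 events with and without hospitalization.

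**What to change.** Reconcile the 10.31 sentence, its table and 10.4, including the instruction in 10.4 to report any serious event at once, so that one grade limit applies to each term.

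Changing Any Grade to Grades 1-3 throughout the table would match the governing sentence. If the sponsor intends a wider exemption for some terms, the change should be made at least for ALT, AST and alkaline phosphatase, and the sentence should then say that the other 25 - 3 = 22 terms are exempt at any grade and why.

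Make all 12 unlisted terms agree with Section 15, either by removing them from the table or by adding them to Section 15 where the brochure supports it. Correcting only the most striking ones would leave the same inconsistency for the rest.

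The cost is a table and text edit in an amendment, and a few more expedited reports.

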10.5 Other Required Reporting

- 10.51 Adverse events to be graded at each evaluation and pretreatment symptoms/conditions to be evaluated at baseline per the CTCAE v4.0 grading unless otherwise stated in the table below:

System Organ Class (SOC)	Adverse event/Symptoms	Baseline	Each evaluation
Gastrointestinal disorders	Diarrhea	# stools per day	X
	Nausea	X	X
	Vomiting	X	X
General Disorders	Fatigue	X	X
	Palmar-plantar erythrodysesthesia syndrome	X	X
Skin and Subcutaneous Tissue Disorders	Rash maculo-papular	X	X
Vascular disorders	Hypertension	X	X

- 10.52 Submit via appropriate Academic and Community Cancer Research United (ACCRU) Case Report Forms (i.e., paper or electronic, as applicable) the following AEs experienced by a patient and not specified in Section 10.5:

- 10.521 Grade 2 AEs deemed *possibly, probably, or definitely* related to the study treatment or procedure.
- 10.522 Grade 3 and 4 AEs regardless of attribution to the study treatment or procedure.
- 10.523 Grade 5 AEs (Deaths)
- 10.5231 Any death within 30 days of the patient's last study treatment or procedure regardless of attribution to the study treatment or procedure.
- 10.5232 Any death more than 30 days after the patient's last study treatment or procedure that is felt to be at least possibly treatment related must also be submitted as a Grade 5 AE, with a CTCAE type and attribution assigned.

